1.1 STUDY DESIGN AND RANDOMIZATION

The LTS16004 study is a long-term, multicenter, follow-up study to determine the safety and efficacy of tolebrutinib. Participants who completed treatment with tolebrutinib in the previous DRI15928 study are eligible for enrollment. Participants will start the treatment as soon as possible after informed consent. The study consists of 2 parts:

Part A: Double-blind period of continued treatment with the respective tolebrutinib dose (ie, 5, 15, 30, or 60 mg/day) administered in the DRI15928 study.

Until the dose of tolebrutinib to be used in Phase 3 is determined, participants will continue treatment with their same tolebrutinib dose used in the DRI15928 study. Cohort 1 of the DRI15928 study that exits the trial receiving placebo from Weeks 13 to 16 will receive the active treatment dose assigned to them at randomization and administered during Weeks 1 to 12. The double-blind will be maintained until the selection of the Phase 3 dose is made.

Part B: Open-label period of a single-group treatment with the Phase 3 dose, selected as 60 mg/day tolebrutinib.

All participants providing consent to Part B of the study will be switched to open-label treatment with the selected dose. If the participant is not willing to switch to the selected dose of tolebrutinib, the participant will be withdrawn from the study and a follow-up visit will be performed 4 to 6 weeks after the last study intervention.

After the end of this study, participants who successfully complete the trial on tolebrutinib may be offered the option to participate in a Phase 3 LTS study for up to an additional 3 years, or until tolebrutinib is approved in their respective country, whichever comes first. If this program is terminated earlier, other available RMS treatments will need to be considered at discretion of the treating physician.

An IDMC will follow safety data periodically as detailed in the DMC charter.

1.2 OBJECTIVES

1.2.1 Primary objectives

The primary objective of this study is to determine the long-term safety and tolerability of tolebrutinib in RMS patients.

1.2.2 Secondary objectives

The secondary objective of this study is to evaluate efficacy of tolebrutinib on disease activity, assessed by clinical and imaging methods.

1.3 DETERMINATION OF SAMPLE SIZE

There are no sample size calculations for this long-term extension study.

All participants who completed the DRI15928 study were eligible for enrollment in the LTS16004 study. The Sponsor enrolled 130 participants in the DRI15928 study, 129 completed the study treatment, and 126 enrolled in LTS16004.

1.4 STUDY PLAN

The SoA for up to Year 1, during Years 2 to 4, and for Year 5 can be found in Section 1.3 of the study protocol, Tables 1-3. The graphical study design is provided in Figure 1 of the study protocol.

1.5 MODIFICATIONS TO THE STATISTICAL SECTION OF THE PROTOCOL

The major changes in the protocol which are related to the statistical analysis are listed in this section.

Amendment Number	Approval Date	Description of statistical changes	Rationale
4	28-Oct-2020	Appendix 10 was added, containing contingency measures for a regional or national emergency that is declared by a governmental agency. Section 10.9.4 mentioned the methods of handling the impact of the emergency such as missing data would be detailed in the Statistical Analysis Plan.	To account for the impact of regional or national emergency such as COVID-19

1.6 STATISTICAL MODIFICATIONS MADE IN THE STATISTICAL ANALYSIS PLAN

SAP Version	Approval Date	Changes	Rationale
2	10-Jul-2023	Changed SAR442168 to tolebrutinib throughout. Added opportunity to enroll in Phase 3 LTS17043 after completing the current study.	Subsequent availability of the INN - international nonproprietary name could be added to abbreviations. Since the LTS16004 study will end in 2024 and the phase 3 LTS is scheduled to start in 2024, participants will have the opportunity to continue tolebrutinib treatment.

SAP Version	Approval Date	Changes	Rationale
		Deleted study schedule and graphical study design.	They are already detailed in the protocol and so replaced with a reference to the protocol sections.
		Added missing MRI parameters as efficacy endpoints and the corresponding analysis methods.	Several exploratory MRI parameters were missed in the previous SAP version.
		Added safety findings on MRI to safety endpoints. Added the contents about reporting of safety findings from MRI.	Based on Protocol Amendment 02 & 05.
		Added summary tables for AEs occurring in Part A only.	To assess for any dose relationship in adverse events in Part A.
		Extended disposition summary.	To cover treatment and study status in both parts (A and B) of the study.
		Removed the miTT DRI15928+LTS16004 population in Section 2.3.1	Considering that miTT LTS16004 population is already defined and that there is no difference between these two populations.
		Added supplementary analysis of ARR on 60 mg tolebrutinib including data from all dose groups after the switch to the 60 mg dose.	Since all participants switch to tolebrutinib 60 mg in Part B, a better estimate of the ARR at this dose level can be provided by grouping participants together.
		Added a summary of COVID-19 related AEs in Section 2.4.5.1	Grouping PTs to get the overall incidence of COVID-19.
		Added methods of addressing missing data issue due to regional or national emergency.	According to Protocol Amendment 04.
		Added a table describing the selection criterion for each AESI category	To give a more explicit description of all AESI categories and to be aligned with the SAPs of the tolebrutinib phase 3 studies.
		Reformatted existing content when necessary. Did minor, editorial, stylistic changes as necessary. Updated table of contents, section numbers, abbreviations as necessary.	Accordance with Sponsor's standards.

2 STATISTICAL AND ANALYTICAL PROCEDURES

2.1 ANALYSIS ENDPOINTS

2.1.1 Demographic and baseline characteristics

The baseline value is defined as the baseline value from the DRI15928 study. Data for demographic and baseline characteristics will be from study DRI15928 database for participants who enrolled in LTS16004.

All baseline safety and efficacy parameters (apart from those listed below) are presented along with the on-treatment summary statistics in the safety and efficacy sections.

Demographic characteristics

Demographic variables are gender (Male, Female), race (Caucasian/white, Black, Asian/Oriental, American Indian or Alaska Native, Native Hawaiian or other Pacific Island, other), age in years (quantitative and qualitative variable: ≤ 40 , > 40 years), and ethnicity (Hispanic, non-Hispanic).

Medical or surgical history

Medical and surgical history data in DRI15928 will be recoded to PT and associated primary SOC using the version of MedDRA in use at Sanofi at the time of LTS16004 database lock. Any new past and/ or concomitant diseases or past surgeries since the end of DRI15928 will also be included.

Substance use - alcohol habit

The frequency of alcohol use in the last 12 months prior to entry into DRI15928.

Multiple sclerosis history and disease characteristics at baseline

MS history and disease characteristics as defined in DRI15928 including time since first symptoms of MS (years), time since diagnosis of MS (years), time since most recent relapse onset (months), MS type (relapsing remitting, secondary progressive), number of relapse(s) within the past year and within the past 2 years (quantitative and qualitative: 0, 1, 2, ≥ 3), baseline EDSS score (quantitative and qualitative). All are relative to DRI15928 randomization visit.

MRI parameters at baseline

MRI parameters at DRI15928 baseline include count of Gd-enhancing T1 hyperintense, T2, and T1 non-enhancing (hypointense) lesions, volume of T2 and T1 non-enhancing (hypointense) lesions, and normalized brain, cerebral cortex, and thalamic volume.

2.1.2 Prior and concomitant medications

All medications ongoing at the end of the DRI15928 study, new medications taken since the end of the DRI15928 study, and any medications taken during the LTS16004 study including MS related treatment(s) are to be reported in the eCRF pages.

All medications will be coded using the WHO-DD using the version currently in effect at Sanofi at the time of database lock.

Prior medications are those the participant used prior to first IMP intake in LTS16004, including those in both DRI15928 and LTS16004. These prior medications can be discontinued before first dosing or can be ongoing during treatment phase.

Concomitant medications are those the participant used at any time during the LTS16004 treatment period, from the first IMP intake in LTS16004 to the day of last IMP intake in LTS16004. A given medication can be classified both as a prior medication and as a concomitant medication. Any technical details related to computation, dates, imputation for missing dates are described in [Section 2.5](#).

2.1.3 Efficacy endpoints

Baseline for efficacy endpoints assessed for long-term tolebrutinib treatment by change from baseline is defined as the last non-missing value prior to the first administration of randomized study intervention in the DRI15928 study, unless otherwise specified. All efficacy evaluations up to the closeout measurement will be included for analysis unless otherwise specified.

2.1.3.1 MRI parameters

For MRI parameters, data from both DRI15928 and LTS16004 will be examined. The last MRI obtained in the DRI15928 study, if performed within 6 weeks prior to Day 1 of the LTS16004 study, will be acceptable as the Day 1 MRI for the LTS16004 study.

MRI assessment will be performed at visits as specified in the protocol [Section 1.3](#) SoA.

MRI parameters include:

- Number of new Gd-enhancing T1 hyperintense lesions (secondary)
- Number of new or enlarging T2 lesions (secondary)
- Total number of Gd-enhancing T1-hyperintense lesions (secondary)
- Volume of T2 and new/enlarging T2 lesions (tertiary/exploratory)
- Number of new T1 non-enhancing (hypointense) lesions (tertiary/exploratory)
- Volume of T1 non-enhancing (hypointense) lesions (tertiary/exploratory)
- Percent change from baseline in sum of brain volume (tertiary/exploratory)
- Percent change from baseline in sum of thalamus volume (tertiary/exploratory)

- Percent change from baseline in sum of cerebral cortex volume (tertiary/exploratory)
- Change in myelin integrity and other features of MRI lesions as measured by magnetization transfer ratio (MTR) and susceptibility-weighted imaging MRI (tertiary/exploratory):
 - Number of slowly enlarging lesions
 - Volume of slowly enlarging lesions
 - Number of phase rim lesions
 - MTR recovery in Gd-enhancing lesions
- Proportion of participants with no new MRI disease activity through the end of the study defined as 0 new Gd-enhancing T1-hyperintense lesions and 0 new or enlarging T2 lesions. (tertiary/exploratory)
- Normalized T1 intensity evolution in slowly evolving lesions
- Normalized T1 intensity evolution in screening unenhancing T2 lesions
- Normalized T1 intensity evolution in phase rim regions of interest

In the DRI15928 study and the LTS16004 study Part A the central reader is blinded and in the LTS16004 study Part B the central reader is not blinded.

2.1.3.2 MS relapse

MS relapse events are clinical events that met the protocol defined criteria (protocol Section 8.1.2.2).

ARR:

Defined as the number of confirmed relapses per participant-year (secondary) in LTS16004.

Proportion of relapse free participants

The proportion of participants without confirmed relapse in LTS16004 will be estimated based on the Kaplan-Meier curve at yearly time points (1, 2, 3, 4 and 5 years since first IMP in LTS16004).

2.1.3.3 EDSS

EDSS is an ordinal clinical rating scale which ranges from 0 (normal neurologic examination) to 10 (death due to MS) in half-point increments. EDSS consists in rating of 7 functional systems (pyramidal, cerebellar, brainstem, sensory, bowel and bladder, visual rating, and cerebral functions) and ambulation. Change from baseline at each visit in LTS16004 will be presented (secondary).

[REDACTED]

[REDACTED]

2.1.4 Safety endpoints

The safety analyses will be based on the reported AEs, including safety findings on MRI, and other safety information, such as clinical laboratory, ECG, vital signs, and C-SSRS data collected in LTS16004.

Magnetic resonance imaging scans should be reviewed locally for any non-MS pathology. In case of such findings, the relevant information needs to be provided to the Investigator for appropriate safety reporting and to ensure the appropriate management of the participant's identified safety finding. When available, a diagnosis of pathology as a cause of such MRI findings or the findings themselves will be reported as an AE until the diagnosis is clear.

MS relapses are exempt from being reported as AE/SAE unless, in the judgment of the Investigator, it is unusually severe or medically unexpected. MS relapses are collected on the eCRF and analyzed as part of the efficacy analyses.

Observation periods

In general, there should be no pretreatment AEs in the LTS16004 study since participants were to roll directly into LTS16004 after completing the DRI15928 study. However, in case there is a gap, the pre-treatment period for the LTS16004 study is defined as the time from signing the ICF until first IMP intake in the LTS16004 study.

The on-treatment period is from first administration of tolebrutinib in the LTS16004 study to the last administration +10 days, including both Part A and Part B treatment periods.

The post-treatment period, if applicable, is from the end of the on-treatment period to the end of the follow-up in LTS16004.

The on-study period is from signing the ICF to the end of follow-up in the LTS16004 study.

2.1.4.1 Adverse events variables

Adverse event observation period

Pre-treatment adverse events are AEs that developed, worsened, or became serious during the pre-treatment period.

TEAEs are AEs that developed, worsened, or became serious during the on-treatment period.

AEs for Part A are AEs that developed, worsened, or became serious during Part A of the study.

Post-treatment AEs are events that developed, worsened, or became serious during the post-treatment period.

All adverse events including SAEs and AESIs will be coded to a LLT, PT, HLT, HLG, and associated primary SOC using the version of MedDRA currently in effect at Sanofi at the time of database lock.

Selection criterion for each AESI category is listed as below. The AESI categories are described in the protocol Section 8.3.1.

Table 1 - Selection criterion for each AESI category

AESIs	Selection
Pregnancy of a female participant entered in a study as well as pregnancy occurring in a female partner of a male participant entered in a study with IMP/NIMP	'Pregnancy' or 'Partner Pregnancy' ticked on the Pregnancy eCRF.
Symptomatic overdose (serious or nonserious) with IMP/NIMP	AECAT="OVERDOSE DATA"; must be symptomatic
Increase in ALT - increase of ALT > 3 x ULN	AECAT="ALT INCREASE DATA" and AESI check box marked.
ECG observation of atrial fibrillation or atrial flutter	CMQ30003 for selection and AESI check box marked.
Severe infection that may or may not meet seriousness criteria (eg, a severe opportunistic infection)	SOC of Infections and Infestations, intensity being severe and AESI check box marked.
Moderate or severe hemorrhagic events, including but not limited to symptomatic bleeding, bleeding in a critical area or organ such as the CNS, or intraocular bleeding.	SMQNAME="Haemorrhage terms (excl laboratory terms)" for selection, intensity being moderate or severe, and AESI check box marked.
Thrombocytopenia, platelet count <75 x 10 ⁹ /L	PT="Thrombocytopenia" and AESI check box marked.

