One participant in the MAD 60 mg cohort was unblinded due to decreased platelet count. Platelet counts will therefore be monitored during the study. Reduction in platelets observed during the study did not exceed $100 \times 10^9/L$. SAR442168 is rapidly absorbed (time to reach maximum observed concentration [t_{max}] is close to 1 hour) and rapidly eliminated (elimination half-life [$t_{1/2}$] was <2.5 hours). When [redacted] mg SAR442168 oral solution was administered with a moderate-fat meal, a mild food effect was observed with an increase of 1.55-fold in AUC and 1.37-fold in maximum serum concentration (C_{max}) (n = 4 participants). Covalent binding enables a durable pharmacodynamic (PD) effect, and steady state is achieved within 5 to 10 days. Cerebrospinal fluid exposure has been confirmed in humans with CSF concentrations of approximately 1.87 ng/mL at 2 hours, which is more than 10 times greater than the cell-based IC_{50} of 0.18 ng/mL.

Phase 1 relative bioavailability and food effect for a SAR442168 tablet formulation:

A single-center, 3-period, open-label, randomized, complete crossover study was performed to assess the relative bioavailability and food effect for a novel SAR442168 immediate release, oral solid tablet formulation compared to a reference oral liquid formulation that was used in a Phase 1 SAD/MAD study. This study was performed in a cohort of 14 healthy participants.

[redacted] milligrams of SAR442168 oral solution had a similar bioavailability to [redacted] mg SAR442168 as [redacted] tablets in fasted conditions with a ratio (tablet/solution) of 1.0 in area under the concentration-time curve until the last quantifiable concentration (AUC_{last}) and 1.03 in C_{max} for SAR442168. When SAR442168 tablets were administered with a high fat meal, a moderate food effect was observed at [redacted] mg with an increase of 1.80-fold in AUC_{last} and no effect on C_{max} (a 1.18-fold increase) for SAR442168.

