8.3 ADVERSE EVENTS AND SERIOUS ADVERSE EVENTS

8.3.1 Adverse event of special interest

An AESI is an AE (serious or nonserious) of scientific and medical concern specific to the Sponsor's product or program, for which ongoing monitoring and immediate notification by the Investigator to the Sponsor is required. Such events may require further investigation in order to characterize and understand them. Adverse events of special interest may be added, modified or removed during a study by protocol amendment.

- Pregnancy of a female participant entered in a study as well as pregnancy occurring in a female partner of a male participant entered in a study with IMP/NIMP
 - Pregnancy occurring in a female participant entered in the clinical trial or in a female partner of a male participant entered in the clinical trial. It will be qualified as an SAE only if it fulfills one of the seriousness criteria (see Appendix 3 [[Section 10.3](#)]),
 - In the event of pregnancy in a female participant, IMP should be discontinued,
 - Follow-up of the pregnancy in a female participant or in a female partner of a male participant is mandatory until the outcome has been determined (See Appendix 4 [[Section 10.4](#)]).
- Symptomatic overdose (serious or nonserious) with IMP/ NIMP
 - An overdose (accidental or intentional) with the IMP/NIMP is an event suspected by the Investigator or spontaneously notified by the participant (not based on systematic pills count) and defined as at least twice the intended dose within the intended therapeutic interval (eg, ≥ 2 tablets of the IMP within a 12-hour interval).
- Increase in alanine transaminase (ALT)
 - Any increase of ALT $>3 \times$ upper limit of normal (ULN).
- Other project specific AESI(s)
 - ECG observation of atrial fibrillation or atrial flutter
 - Severe infection that may or may not meet seriousness criteria (eg, a severe opportunistic infection)
 - Moderate or severe hemorrhagic events, including but not limited to symptomatic bleeding, bleeding in a critical area or organ such as the CNS, or intraocular bleeding.
 - Thrombocytopenia, platelet count $<75 \times 10^9/L$ (see Appendix 6, [Section 10.6](#) for management flow chart).

The definitions of AEs and SAEs can be found in Appendix 3 ([Section 10.3](#)).

Adverse events will be reported by the participant (or, when appropriate, by a caregiver, surrogate, or the participant's legally authorized representative).

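### SAP Table 1 picks out the thrombocytopenia AESI by one preferred term plus the AESI box, so a qualifying, ticked event coded to another platelet-decrease term would lose its AESI classification

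*SAP*

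**What the plan says.** Protocol 8.3.1 lists this AESI as "Thrombocytopenia, platelet count" below 75 x 10^9/L. The same section makes every AESI an adverse event first: "An AESI is an AE (serious or nonserious) of scientific and medical concern".

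SAP 2.1.4.1 states how terms are assigned: "All adverse events including SAEs and AESIs will be coded to a LLT, PT, HLT, HLG, and associated primary SOC", in the MedDRA version in force at database lock. SAP Table 1 then gives one selection criterion per AESI category. The thrombocytopenia row repeats the count threshold in its label, but its criterion is "PT='Thrombocytopenia' and AESI check box marked".

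Three neighbouring rows use grouped terms:
- Atrial fibrillation or flutter: "CMQ30003 for selection and AESI check box marked".
- Severe infection: "SOC of Infections and Infestations, intensity being severe and AESI check box marked".
- Haemorrhage: "SMQNAME='Haemorrhage terms (excl laboratory terms)' for selection", with intensity and the box added.

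The ALT row uses an eCRF category and the box. The pregnancy row uses an eCRF form, and the overdose row an eCRF category with a requirement for symptoms.

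SAP 2.4.5.1 plans a table of treatment-emergent AESIs by category and PT, marked to be repeated for Part A, and a listing of all AESIs by category.

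**The concern.** The category is defined by a laboratory value but selected by a word. The threshold enters only through the investigator's tick, and the coded term can then overrule the tick. An investigator may see a count below 75 x 10^9/L, report it and mark it as an AESI, and the event still fails selection if the reported wording codes elsewhere.

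Other wording is permitted. Protocol Appendix 3 accepts an abnormal laboratory finding as an adverse event and asks for a diagnosis only where possible. The protocol's own Background (2.2) describes a platelet fall differently: "One participant in the MAD 60 mg cohort was unblinded due to decreased platelet count".

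Safety is the primary objective, and Protocol 2.3 lists cytopenia including thrombocytopenia. Readers will take the AESI row as the incidence of counts below 75 x 10^9/L. Part A is the only period in which four doses run side by side, and SAP 2.4.5 uses Part A summaries to look for dose-related trends. Protocol 4.3 reports few AESIs of any kind in the preceding study. If numbers stay small, one lost case could turn one into none.

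**Working it through.** The plan gives no figure for this point, so there is nothing to reproduce. The check is a reading of the rule, followed by simple arithmetic for scale.

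**Step 1. Apply the rule to every case.** Take an event with a count below 75 x 10^9/L that was reported as an adverse event.

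| Coded PT | AESI box | Rule as written | PT group, box kept |
|---|---|---|---|
| Thrombocytopenia | ticked | selected | selected |
| Another platelet-decrease PT | ticked | **not selected** | selected |
| Thrombocytopenia | not ticked | not selected | not selected |
| Another platelet-decrease PT | not ticked | not selected | not selected |

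Only the second row changes. Widening the terms does not bring in unticked events.

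**Step 2. Trace the outputs.** Table 1 is the only stated rule for membership of an AESI category. The SAP has no residual category for ticked events that fit no row, and no selection by platelet value. The AESI table, its Part A version and the AESI listing are all organised by category, so an event without a category has no place in them.

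**Step 3. See where the event remains.**
- It stays in the table of all TEAEs by system organ class and PT, which is also produced for Part A by dose (SAP 2.4.5.1).
- The count may appear in the tables of potentially clinically significant abnormalities. SAP 2.4.5 and 2.5.4 both let unscheduled values count there, and 2.4.5 also includes repeats. The platelet threshold is not given in the documents.
- By-visit summaries cannot be relied on either way. SAP 2.4.5 assigns unscheduled values to visit windows for these summaries, and SAP 2.5.4 leaves unscheduled laboratory values out of them. No argument here rests on this.

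**Step 4. Compare the rows.** This is the only category limited to one PT. The nearest comparator is ALT, also defined by a laboratory threshold, and its rule has no PT condition.

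**Step 5. Scale.** The denominator is the 126 participants enrolled (SAP 1.3), taken as an approximation to the safety population.
- Overall: 1/126 = 0.79%.
- By dose group, assuming four equal groups: 126/4 = 31.5, and 1/31.5 = 3.17%.

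**Step 6. Chance of losing at least one event.** Let q be the share of qualifying, ticked events coded to another PT, and m the number of such events, treated as independent. The chance is 1 - (1 - q)^m. Neither q nor m is in the documents, so the table only shows a range.

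| Assumed q | m = 2 | m = 3 |
|---|---|---|
| 0 | 0 | 0 |
| 0.10 | 1 - 0.90^2 = 0.19 | 1 - 0.90^3 = 0.27 |
| 0.25 | 1 - 0.75^2 = 0.44 | 1 - 0.75^3 = 0.58 |
| 0.50 | 1 - 0.50^2 = 0.75 | 1 - 0.50^3 = 0.88 |

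**The case against.** The strongest reply is that the case may never arise. Protocol 8.3.1 names the AESI thrombocytopenia. Appendix 6 heads its algorithm with that word, uses it for adverse event recording, and makes the actions required. Appendix 3 asks for the diagnosis wherever possible. An investigator who ticks the box is applying a definition that supplies the term. The documents list no MedDRA platelet terms and do not show that any particular wording codes apart. This stands, and it is why no number of lost events is claimed.

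Two pieces of support are also thin. The Phase 1 case shows only that other wording is in use. The protocol adds that platelet reductions did not exceed 100 x 10^9/L, which is ambiguous and does not show a count below 75. The haemorrhage query's name shows a term set that leaves out laboratory terms, but says nothing about platelet terms.

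A broad clinical concept such as infection needs a wider net than one named cytopenia, and SAP 1.6 says Table 1 was aligned with the Phase 3 SAPs. That explains the row. It does not remove the mismatch with the definition, and the ALT row shows that a narrow, laboratory-defined category can be selected without a PT.

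A reader might infer two stronger things. One is that low platelet counts would vanish from the report; the TEAE tables, including the Part A version, rule that out for any event reported as treatment-emergent. The other is that the rule is at fault for counts below 75 with no adverse event record. By the protocol's definition an AESI is an adverse event, so that is mainly a reporting matter and not a defect of this selection rule.

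**Conclusion.** The point holds as a misclassification risk confined to three outputs: the AESI table by category and PT, its Part A version and the AESI listing. On the plain text, a qualifying and ticked event under another platelet-decrease PT is left out of all three. This is a stated rule that departs from the protocol definition, not a missing detail.

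The reading of the rule is firm; the consequence is not. The number affected is unknown and may be zero. Each affected participant would change the AESI incidence by 0.8 points overall, or by about 3.2 points in a dose group, on the assumptions that the safety population is close to 126 and the groups are equal. No tests are planned, so the effect is on descriptive counts and on the Part A dose comparison for this category. The TEAE tables soften the loss but do not replace the AESI row, because they do not show which platelet events were below 75 x 10^9/L. The change should be made because it is nearly free, not because harm has been shown.

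**What to change.** In the thrombocytopenia row of SAP Table 1, replace the single PT with a prespecified group of platelet-decrease PTs. Confirm the list in the MedDRA version in force at database lock, and keep the requirement that the AESI box is marked. The AESI table by PT will then show which term each event carried.

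The cost is one SAP table row and a small programming change on data already collected. There is no protocol amendment. The row may differ slightly from the Phase 3 SAPs, which a footnote can explain, and AESI counts may rise slightly.

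Optional, and not needed for the fix: a listing that reconciles platelet counts below 75 x 10^9/L with AESI records. Laboratory-only cases would be shown there and not counted as AESIs.
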